8.1. Definitions

8.1.1. Adverse Event and Adverse Device Effects

Adverse Event: any untoward medical occurrence, unintended disease or injury, or untoward clinical signs (including abnormal laboratory findings) in subjects, users or other persons, whether or not related to the investigational medical device.

NOTE 1: This definition includes events related to the investigational medical device.

NOTE 2: This definition includes events related to the procedures involved.

NOTE 3: For users or other persons, this definition is restricted to events related to investigational medical devices.

Adverse Device Effect: adverse event related to the use of an investigational medical device.

NOTE 1: This definition includes adverse events resulting from insufficient or inadequate instructions for use, deployment, implantation, installation, or operation, or any malfunction of the investigational medical device.

NOTE 2: This definition includes any event resulting from use error or from intentional misuse of the investigational medical device.

Unanticipated Adverse Device Effect: adverse event related to the use of an investigational medical device.

NOTE 1: This definition includes adverse events resulting from insufficient or inadequate instructions for use, deployment, implantation, installation, or operation, or any malfunction of the investigational medical device.

NOTE 2: This definition may include any event resulting from use error or from intentional misuse of the investigational medical device.

8.1.2. Device Deficiency

Device Deficiency: inadequacy of a medical device with respect to its identity, quality, durability, reliability, safety or performance.

NOTE: Device deficiencies include malfunctions, use errors, and inadequate labelling.

8.1.3. Serious Adverse Event and Serious Adverse Device Effects

Serious adverse event (SAE): an adverse event that

1. Led to death,
2. Led to serious deterioration in the health of the subject, that either resulted in
 - a. a life-threatening illness or injury, or
 - b. a permanent impairment of a body structure or a body function, or
 - c. in-patient or prolonged hospitalization (>24 hours), or
 - d. medical or surgical intervention to prevent life-threatening illness or injury or permanent impairment to a body structure or a body function,
3. Led to fetal distress, fetal death or a congenital abnormality or birth defect.

Note: Preplanned events of hospitalization or surgical interventions will not be recorded as an SAE.

Serious adverse device effect (SADE): adverse device effect that has resulted in any of the consequences characteristic of a serious adverse event.

8.1.4. Unanticipated (Serious) Adverse Device Effect (U(S)ADE)

Anticipated serious adverse device effect (ASADE): is an effect which by its nature, incidence, severity or outcome has been identified in the risk analysis report.

Unanticipated serious adverse device effect (USADE): serious adverse device effect which by its nature, incidence, severity or outcome has not been identified in the current version of the risk analysis report and section 6.2.

8.2. Device relatedness

The potential relationship of the event to the investigational device or procedure will be judged by the investigator. The relation will be based on the following definitions:

- Related - Definite causal relationship
- Probable - Good reasons and sufficient documentation to assume a causal relationship
- Possible - A causal relationship is conceivable and cannot be dismissed
- Unlikely - The event is most likely related to an etiology other than the investigational product administration
- Unrelated - Definitely no causal relationship

Events classified as related, probable and possible are considered related and need to be reported. Events classified as unlikely and unrelated are not considered related and do not need to be reported. See section 8.4 for more details.

8.3. Severity

The assessment of severity is a clinical determination of the intensity of an adverse event. The severity assessment for a clinical adverse event should be completed using the following definitions as guidelines:

- Mild – Transient symptoms, no interference with the patient's daily activities
- Moderate – Marked symptoms, moderate interference with the patient's daily activities
- Severe- Considerable interference with the patient's daily activities, which is unacceptable

8.4. Reporting

8.4.1. Reporting Requirements

For the purposes of study, only device-related events ((S)(U)ADEs), procedure-related events and device deficiencies will be reported. (S)ADE, procedure-related events and device deficiency collection will commence once the subject has provided written informed consent and the patient has entered OA Imago scanning room.

8.4.2. Reporting to Sponsor

All adverse events classified as serious adverse device effects or (SADEs) as well as serious unanticipated adverse device effects (SUADE) and possibly-, probably- or definitely-related to the device need to be reported to Seno within 24 hours of learning of the event, using the EDC system.

8.4.3. Reporting to Regulatory Authorities

Events will be notified to the IRB per IRB guidelines and to FDA in accordance with FDA Guidelines.

9. IMAGING CORE LAB

To ensure consistency, the assessment of all imaging studies including **Imagio** will be managed by an independent Imaging Core Lab (ICL) to perform quality assurance review of collected images.

The Imaging Core Lab participating in this study will be:

Medical Metrics

[name]

[name]

[contact]

10. MONITORING

Monitoring of the study will be performed in accordance with FDA guidelines. Monitoring including source data verification should be routinely performed prior to the transfer of the data to Data Management.

Site monitoring visits will be performed by the Seno or Seno's representatives on a regular basis in accordance with the Monitoring Plan. During monitoring visits, data entered in the eCRF will be source verified for accuracy and completeness. In addition, protocol compliance and compliance with FDA regulations will be verified. The monitor should have direct access to source data for verification purposes. The eCRF data will be compared with data in the subjects' medical records. Such verification is essential to quality control.

The Sponsor expects that, during monitoring visits, the study coordinator and Principal Investigator will be available, the source documentation will be available and that a suitable environment will be provided for review of study documents.

11. AUDITS AND INSPECTIONS

Independent auditors from the Seno or Seno's representative may request access to all study records, including source documents for inspection, audit and/or copying in keeping with applicable regulations. The Principal Investigator should immediately notify the sponsor of an upcoming regulatory authority inspection.

12. STATISTICAL METHODS

12.1. Study Hypotheses

The overall hypothesis motivating this pilot feasibility study is that **Imagio OA** can provide incremental improvements in the clinical classification of thyroid nodules into benign and not benign and into finder subclasses. To evaluate this hypothesis, a heterogeneous sample of at least 50 patients will be evaluated and steps will be taken to optimize software parameter and clinical guidelines. Initial evaluation of reliability and validity will be obtained by having three independent readers make predictions first with conventional gold standard methods and then augmented with **Imagio OA**. These results will be summarized using conventional measures of diagnostic utility, with emphasis on incremental improvement in specificity, the percentage of correct down grades, the percentage of correct upgrades, and the negative likelihood ratio. When appropriate, statistical estimates will be reported along with 95% confidence intervals.

12.2. Analysis Populations

All analyses will be performed with the intention to diagnose (ITD) study population which consists of all subjects coming in for their scheduled Imaging Visit, having Imago OA data declared evaluable, and having a biopsy of at least one nodule with evaluable cytology/histology results.

12.3. Demographics and Baseline Characteristics

The age, race, ethnicity, will be presented using descriptive statistics for the overall ITD population, by sites diagnostic status (benign, malignant).

12.4. Sample Size Discussion

Based on experience with feasibility studies performed for evaluation of breast nodules, the sample size for this feasibility study is driven by software and clinical rule development needs. From this perspective, it was concluded that the reference set should include a minimum of 50 thyroid nodules with adequate cytopathology or histopathology for diagnosis that include: 10 papillary thyroid carcinomas minimum, 10 Follicular neoplasms, and 30 benign nodules that include at least 5 Hashimoto nodules. Therefore, a total of 50 thyroid nodules will form the initial software development reference set. Based on the rate of non-benign nodules, it is expected that about twice the number of patients needed will have to be evaluated to obtain the minimum sample sizes noted above. Therefore, the target evaluable sample size is N=100. The 'extra' benign nodules enrolled are important because they will increase the statistical precision of key measures of predictive value including the increment improvement in specificity. It is estimated that roughly 10% of enrolled patients may have thyroid nodules for which FNAB cytopathology is inadequate (after initial and potential subsequent FNA) and in whom surgical excision is not performed cannot be included in the study and will be replaced. To account for this N=110 nodules will be enrolled. As discussed below, this study will rely on the TI-RAD risk categorization (categories 1-5). After 50 nodules are identified as evaluable, the clinical status will be summarized, and if it is projected that there will be too few non-benign nodules, subsequent enrollment will be restricted to TI-RAD categories 3, 4, and 5.

12.5. Analyses

The following outlines the steps to be taken to develop and tune the image creation and colorization algorithm and to develop the guidelines and interpretations rules that will be subsequently applied by three independent readers. The steps will be performed collaboratively by the software engineer and Medical Director, with potential input at earlier stages from the site radiologists.

DEVELOPMENT OF GUIDELINES, INTERPRETATION RULES AND ESTIMATORS

1. Images and data will provide a basis for algorithm finalization, potential instrument improvements, the development of guidelines for interpretation of OA studies of thyroid nodules. Permit Imago OA optimizations with respect to specific parameters (e.g. illumination and detection conditions, laser pulse repetition rate, sound propagation characteristics, etc.). Optimizations may be different for thyroid nodules and for suspicious cervical lymph nodes.
2. Compare *in vivo* opto-acoustic images with those obtained from standard diagnostic thyroid ultrasound, color Doppler imaging (CDI), power Doppler imaging (PDI), strain elastography (SE), or shear wave elastography (SWE).

3. Compare the in vivo opto-acoustic features with those obtained from standard diagnostic thyroid ultrasound color Doppler imaging (CDI), power Doppler imaging (PDI), strain elastography (SE), or shear wave elastography (SWE).
4. Compare findings of conventional imaging modalities and those of opto-acoustic imaging with biopsy results for nodule size, location, type, and stage.
5. Develop Imago-based estimators for thyroid use.

Once the above steps are completed, quantitative analyses will be performed similar to those performed during previous pilot studies of the Imago OA in breast imaging. The predictive and clinical classification results based on the optimal results determined from the process above will be summarized, as will the results based on application of the preliminary guidelines by three independent raters. The primary summary of results will include five by five cross-tabulation of initial TI-RAD category by TI-RAD category based Imago OA stratified by clinical status (e.g., benign vs not benign and papillary thyroid carcinomas vs Follicular neoplasms, and benign nodules. These tables will be used to determine the percentages of correct downgrades (among benign nodules) and correct upgrades (among non-benign nodules). Specificity will be determined as the percentage of benign nodules with a final TI-RAD score of 1 or 2 since these risk categories generally would not result in further invasive evaluation unless patient requested. The improvement in specificity comparing initial TI-RAD to TI-RAD after Imago OA is considered a primary endpoint in this study. Sensitivity will be similarly evaluated. Where appropriate, 95% confidence intervals will be determined to evaluate statistical precision of the estimates. The results will also be expressed in terms of negative likelihood ratios (NLR) at specific TI-RAD categories. The NLR is the false-negative fraction divided by the true negative fraction at each level of TI-RAD. For dichotomous tests, this is (1-sensitivity) divided by specificity. NLRs as well as positive likelihood ratios represent an effective way to summarize the predictive capacity of diagnostic tests. Pre-test probabilities are converted to pre-test odds (Pre-test Odds = Probability/1-Probability). Post-test Odds for a negative test = Pre-test Odds times NLR. Post-test probability = Post-test Odds / (1 + Post-test Odds). Analyses will be performed for each independent rater and for a consensus rule based on pooling predictions across raters. Weighted Kappa statistics and measures of overall agreement will be used to summarize prediction reliability across rates.

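### Nodules used to tune the OA algorithm and reading rules appear to be evaluated again in the single ITD set, with no dated lock, hold-out or optimism correction, so sensitivity is expected to look too high and NLR too low

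*Combined protocol and SAP*

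**What the plan says.** **Tuning.** Section 12.5 lists the development steps for the image algorithm, the reading guidelines and the estimators. Step 4 brings in the reference standard: "Compare findings of conventional imaging modalities and those of opto-acoustic imaging with biopsy results for nodule size, location, type, and stage". Section 12.4 says that "a total of 50 thyroid nodules will form the initial software development reference set", made up of at least 10 papillary carcinomas, 10 follicular neoplasms and 30 benign nodules.

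**Evaluation.** After the development steps, Section 12.5 states: "The predictive and clinical classification results based on the optimal results determined from the process above will be summarized". It also reports three raters, who use "guidelines and interpretations rules that will be subsequently applied by three independent readers". The planned measures are specificity gain, correct downgrades and upgrades, sensitivity and NLR, with 95% confidence intervals where appropriate.

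**Analysis set.** Section 12.2: "All analyses will be performed with the intention to diagnose (ITD) study population". Section 12.4 gives the nodules beyond the 50 a precision role. The extra "benign nodules enrolled are important because they will increase the statistical precision of key measures of predictive value". They are not described as a validation set.

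**Use of the results.** Section 2.2 makes initial estimates of predictive value a secondary objective, Section 12.1 calls the reads an initial evaluation of reliability and validity, and the last paragraph of Section 1.4 says the results will inform the pivotal study's objectives and endpoints.

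**The concern.** A rule tuned on a set of nodules fits the chance features of that set. Scored on the same nodules, it looks better than it will on new ones. The confidence intervals in Section 12.5 describe sampling error and do not capture this.

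The effect falls unevenly here. Section 12.4 sizes the study around the scarce non-benign group: "it is expected that about twice the number of patients needed will have to be evaluated to obtain the minimum sample sizes noted above". At the minimum counts, all 20 non-benign nodules are development nodules, so sensitivity and the numerator of NLR rest wholly or largely on nodules whose diagnosis helped to shape the rules. Specificity is less exposed because the benign group is larger and, if tuning stops at 50, mostly untuned.

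OA findings do not influence biopsy decisions in this study, so no participant is put at risk. What is at stake is planning: a pivotal study could be designed around a sensitivity or NLR that will not be reproduced.

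**Working it through.** **1. The plan's own counts.** 10 + 10 + 30 = 50 development nodules. 2 × 50 = 100 evaluable. Adding 10% gives 100 × 1.10 = 110, as stated (100/0.90 would give 112, a trivial difference). The plan gives no alpha, power or optimism figure to reproduce.

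**2. Composition at the minimum counts.** Non-benign: 10 + 10 = 20, all in the development set. Benign: 30 in that set, and 100 − 50 = 50 outside it if the rest are the extra benign nodules. So 20 of 20 nodules behind sensitivity are tuned, against 30 of 80 behind specificity.

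**3. Size, by simulation.** The documents give no tuning rule, feature count or classifier, so these are assumptions: 80 benign and 20 non-benign nodules; 6 features; ridge logistic score; 2,000 datasets per scenario; true performance from 4,000 fresh nodules. The null device carries no information; the informative one has an AUC of about 0.80. Optimism = apparent − true, in percentage points.

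| Cut-off rule | Null: sensitivity apparent / true (optimism) | Informative: sensitivity apparent / true (optimism) | Specificity optimism, null / informative |
|---|---|---|---|
| 5% of benign called negative* | 98.7 / 95.1 (3.6) | 99.8 / 99.6 (0.2) | 0.1 / −0.4 |
| 10% of benign called negative* | 97.0 / 90.7 (6.3) | 99.5 / 98.9 (0.6) | 0.7 / −0.3 |
| 0 misses allowed | 100 / 88.5 (11.5) | 100 / 92.1 (7.9) | 1.1 / 0.6 |
| 1 miss allowed | 95.0 / 79.9 (15.1) | 95.0 / 85.0 (10.0) | 1.9 / 0.9 |
| Maximum Youden index | 70.2 / 43.0 (27.2) | 81.4 / 64.9 (16.5) | 6.7 / 4.0 |

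*These rows equal a 5- or 10-point specificity gain only if no benign nodule starts at TI-RADS 1 or 2, that is, if baseline CDU specificity is zero.

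With 3 to 10 features, sensitivity optimism spans 0.1 to 33 points. A linear discriminant with 3 or 6 features and other cut-off rules (24 scenarios) gave sensitivity too high, by about 4 to 27 points, and NLR too low in every scenario.

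**4. Tuning limited to the 50.** Tuning on 30 benign and 20 non-benign, then reporting on 80 benign plus the same 20, gives sensitivity optimism of 4.4 to 23.7 points (null) and 0.7 to 15.3 (informative) across the five rules. Confining tuning to the 50 does not help sensitivity, because the non-benign nodules are the same.

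**5. NLR, informative device.** Section 12.5 defines NLR = (1 − sensitivity)/specificity.
- 0 misses: apparent 0/0.328 = 0; true 0.079/0.322 = 0.25.
- Youden: apparent 0.186/0.768 = 0.24; true 0.351/0.728 = 0.48.

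At an assumed pre-test probability of 20%, the pre-test odds are 0.20/0.80 = 0.25. With 0 misses, the true post-test odds are 0.25 × 0.25 = 0.0625, a risk of 0.0625/1.0625 = 5.9%, against an apparent 0%. With Youden, 0.25 × 0.48 = 0.12 gives 0.12/1.12 = 10.7%, against 0.25 × 0.24 = 0.06, or 0.06/1.06 = 5.7%.

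**6. Can it be corrected?** Ten-fold cross-validation, repeating the fitting and cut-off choice in each fold, came within 2.6 points of the true values in all ten cases in the table. For the informative device with 0 misses, sensitivity/specificity is 100%/33% apparent, 92%/32% true and 91%/34% cross-validated.

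**The case against.** **Re-use is never stated.** Correct. It follows from Sections 12.2, 12.4 and 12.5 read together. If the sponsor intends otherwise, one sentence in Section 12.4 settles it.

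**The order is given and the readers are independent.** Section 12.5 does put development before reading, but gives no date or version for a freeze, and the readers' rules come from the same nodules. It stands that every figure above concerns an assumed automated classifier. The plan describes collaborative rule-writing by the software engineer and Medical Director, and Section 3.2 mentions possibly building on an estimator from a previous study. The figures cannot be read as reader optimism.

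**The size is indeterminate.** This stands. For an informative device with the cut-off at 5% of benign nodules, optimism is 0.2 points. The exact 95% interval for 18/20 is 68% to 99%, wider than any informative-device optimism in the table.

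**The study is openly developmental.** This also stands, and it limits the weight of the point. Section 2.2 speaks of initial estimates from optimised rules, Section 12.5 of preliminary guidelines, and Section 12.5.1 treats sensitivity and NLR as supporting. A reader might infer that apparent values will be carried into the pivotal design as true predictive value; no sentence says so.

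**A reader might also infer that a useless device would usually pass the 5% specificity mark.** That depends on baseline CDU specificity, which the documents do not give. TI-RADS 1 to 5 nodules are enrolled, and restriction to 3 to 5 is only conditional. On 50 untuned benign nodules, a null rule passes in about 72% of trials (0 misses) or 95% (1 miss) at a zero baseline, 28–30% or 61–65% at a 10% baseline, and 8–10% or 28–32% at 20%. These passes occur without any overlap, so they are not evidence for this point.

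**Conclusion.** The concern holds for direction. Followed as written, the plan reports apparent performance, and sensitivity is expected to be too high and NLR too low. The conclusion rests on the inferred re-use and on the non-benign nodules lying wholly or mostly in the development set. The quotas are minimums, so some further non-benign nodules could fall outside it.

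The size is conditional on the assumed six-feature classifier and on the cut-off rule: about 0 to 17 points of sensitivity for an informative device and about 4 to 27 for a null one. The documents do not support reading the primary specificity gain as badly inflated by the overlap, since its optimism is only about 0 to 7 points under the same assumptions. Nor do they support a figure for reader optimism.

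The absence of a sensitivity condition in Section 12.5.1 is a separate issue. Sensitivity, NLR and the five-by-five table stratified by clinical status are already planned, and the table would show non-benign nodules moved down.

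**What to change.** - **Section 12.4:** state which nodules are used for tuning, and whether tuning goes beyond the 50.
- **Section 12.5, lock:** freeze, version and date the algorithm, guidelines, estimators and cut-offs before the three evaluation reads.
- **Section 12.5, labels:** mark all results on tuning nodules as *apparent (development)*.
- **Section 12.5, estimators:** for any quantitative estimator, report cross-validated (for example 10-fold) or bootstrap-corrected sensitivity, specificity and NLR beside the apparent values. Repeat feature choice, fitting and cut-off choice in every fold or resample.
- **Section 12.5, readers:** report results separately for tuned and untuned nodules where the untuned set is not empty. State that human rule-writing and the laser or colorization settings cannot be repeated in folds, so reader sensitivity stays largely uncorrected.

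**Cost.** Wording, a dated record and a little analysis work; no extra patients, visits or reads. The figures will look slightly less favourable, and intervals remain wide with about 20 non-benign nodules. The remedy is partial: it corrects the estimators, while reader results are only locked, labelled and split. If nearly all non-benign nodules are tuned, the untuned reader subset will say little about sensitivity.
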